## **4 INTERIM ANALYSIS**

The data from this study will be summarized periodically to support regulatory submissions, or when further information on the long-term safety and efficacy of BG00012 in the pediatric population is required.

## **5 SAMPLE SIZE JUSTIFICATION**

Because this study is an extension study, the sample size was determined by the number of eligible subjects who completed Study 109MS202.

## **6 STATISTICAL ANALYSIS METHODS**

The statistical software, SAS®, will be used for all summaries and statistical analyses.

Statistical analyses will be descriptive in nature with appropriate measures of variation provided where applicable. For continuous endpoints, summary statistics will generally include the following: number of subjects with data, mean, standard deviation, median, and range. For categorical endpoints, summary statistics will generally include the frequency distribution of the analysis population.

### **6.1 Description of Analytic Methods**

As the study contains a single treatment group, descriptive statistics will be the primary approach to analyze the data.

#### **6.1.1 Summary of Baseline Data**

Baseline data are defined as data collected prior to the administration of BG00012 on Day 1 on study 109MS311, which should be the final visit in study 109MS202. If the final visit in study 109MS202 cannot be used as baseline, Day 1 on study 109MS311 will be considered baseline. Baseline demographics from study 109MS202 will be summarized using only those subjects that continue into study 109MS311. Age will be recalculated based on the date informed consent was signed for study 109MS311.

#### **6.1.2 Accounting of Subjects**

Number of subjects who enrolled into 109MS311 from the previous study, number who received at least one dose of BG00012, number completing treatment, number completing the study, number discontinuing prior to Week 96 and reason for early withdrawal, will be summarized.

#### **6.1.3 Protocol Deviations**

Major and minor protocol deviations identified in the study will be listed.

#### **6.1.4 Demographic and Baseline Characteristics**

Demographic data, including age (in years, at the time of consent to study 109MS311), gender and race category will be summarized for the subjects that enroll into study 109MS311. In addition, baseline height (cm) and weight (kg) will also be presented.

Medical history will be summarized for just those subjects who enrolled in 109MS311 by category using number and percentage of subjects that had experienced certain maladies prior to entering the study. Medical history will include information collected in 109MS202, but for only those subjects who entered 109MS311. Included will be the number of subjects with ongoing or resolved medical/surgical history that have occurred since the subject enrolled in 109MS202.

The MS Pediatric Diagnostic Criteria as defined by Krupp (2013), obtained at screening of study 109MS202, will be summarized for those subjects who enrolled into 109MS311.

MS signs considered typical MS signs and symptoms will be summarized for each area: vision, cognition, coordination/balance, bladder control, bowel, sexual function, and general. In addition, MS signs related to sensory disturbances, motor disturbances, and other will be presented for the population and summarized. Only those subjects who entered 109MS311 will be included in the summaries.

History of MS for the subjects enrolled in 109MS311 will be summarized using information collected prior to study 109MS202. This includes time since first MS diagnosis, time since first symptoms, number of relapses prior to screening in study 109MS202 (prior 12 months, 2 years, and 3 years) and the time since the last relapse prior to 109MS202. In addition, the MS treatment history will be summarized for these subjects in 109MS311 prior to receiving BG00012 in the 109MS202 study.

#### **6.1.5 Concomitant Medications and Non-drug Therapies**

Concomitant medication is defined as prescribed or over-the-counter medications used during the study (on or after Day 1 of 109MS311). The World Health Organization (WHO) Drug Dictionary will be used for coding concomitant medications. The Medical Dictionary for Regulatory Activities (MedDRA) will be used for coding concomitant non-drug therapies.

The number and percentage of subjects taking concomitant medication and receiving non-drug treatments will be summarized.

As the study progresses, a listing of all medications will be periodically reviewed by clinical personnel so as to properly classify concomitant medications as allowed or prohibited.

#### **6.1.6 Exposure to study drug**

Number of days exposed to BG00012 during study 109MS311, total amount of BG00012 received and overall compliance will be summarized. Compliance for each subject is defined as the total amount of BG00012 received divided by the number of days on treatment.

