8. SELECTION OF SUBJECTS

8.1. Inclusion Criteria

To be eligible to participate in this study, candidates must meet the following eligibility criteria at Day 1 or at the timepoint specified in the individual eligibility criterion listed:

1. Ability of parents, legal guardians, and/or subjects to understand the purpose and risks of the study and provide signed and dated informed consent and authorization to use confidential health information in accordance with national and local subject privacy regulations. Subjects will provide assent in addition to the parental or guardian consent, as appropriate, per local regulations.
2. Subjects who completed, as per protocol, the previous BG00012 clinical study 109MS202 and remain on BG00012 treatment at 240 mg BID.
3. All female subjects of childbearing potential and all male subjects must practice effective contraception during the study and for at least 30 days after their last dose of study treatment. For further details of contraceptive requirements for this study, please refer to Section 15.5.

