AE = adverse event; ALT = alanine transaminase; AST = aspartate transaminase; SGOT = serum glutamic oxaloacetic transaminase; SGPT = serum glutamic pyruvic transaminase; ULN = upper limit of normal; WBC = white blood cell.

[Table 4](#) describes the management of lymphocytes <LLN for subjects during and after study treatment.

CONFIDENTIAL

The information contained herein may not be used, disclosed, or published without the written consent of
Biogen MA Inc.

Table 4: Management of Lymphocyte Count <LLN

Laboratory Parameter	Laboratory Result	Required Action
Lymphocyte count on study treatment	<LLN	The Investigator should repeat the test within 2 weeks. If retest confirms that lymphocyte count is <LLN, lymphocyte count should be closely monitored (at least every 4 weeks).
Lymphocyte count on study treatment	<500/mm ³	If lymphocyte count is <500/mm ³ for more than 6 months, study treatment must be permanently discontinued.
Lymphocyte count in subjects who complete, temporarily withhold, or permanently discontinue BG00012 for any reason	<LLN	Subjects will be followed at least every 4 weeks for 24 weeks and then every 3 months (unless clinically indicated more often or at the Investigator's discretion) until the lymphocyte count is \geq LLN ¹ or for 52 weeks after the last dose, or until one of the following occurs: 1) the subject continues on commercial BG00012 following study withdrawal/completion, or 2) the subject is initiated on another MS disease-modifying therapy.

LLN = lower limit of normal; MS = multiple sclerosis.

¹ Lymphocyte counts \geq LLN at 2 consecutive visits are required.

While dosing is withheld, subjects will continue tests and assessments according to [Table 1](#) (and may also undergo additional assessments to evaluate the laboratory abnormality as per the Investigator's standard practice). In addition, subjects (whether on study treatment, having dosing temporarily withheld, or permanently discontinued) must have the abnormal laboratory result rechecked at the central laboratory as follows:

- For all analytes, with the exception of lymphocytes, results will be rechecked at least every 2 weeks until resolution or stabilization of the laboratory value. Depending on the severity and clinical significance of the abnormality, the Investigator may need to perform the retests more frequently.

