11.2.2. Resumption of Study Treatment Dosing

Resumption of BG00012 treatment is to be considered on a case-by-case basis and must be discussed with the Medical Monitor.

CONFIDENTIAL

The information contained herein may not be used, disclosed, or published without the written consent of Biogen MA Inc.

Resumption of study treatment after an interruption

Subjects who are allowed to resume BG00012 dosing after an interruption of ≥ 2 weeks will restart dosing at a reduced dosage for 1 week. Subjects will take one 120-mg capsule BID for 1 week. After 1 week at the reduced dose, subjects will resume taking two 120-mg capsules BID.

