11.2.6. Dosage Reductions

Dosage reduction will be allowed only for subjects **who are unable to tolerate BG00012 treatment due to flushing and/or GI disturbances** (dosage reductions will not be allowed for abnormal laboratory values; for management of abnormal laboratory values, see Sections [11.2.1](#), [11.2.2](#), and [11.2.3](#)). Subjects who do not tolerate BG00012 treatment will reduce their dosage by taking one 120-mg capsule BID for up to 4 weeks. Within 4 weeks at the reduced dosage, subjects will resume taking the full dose of 240 mg (two 120-mg capsules) BID. If the subject is still unable to tolerate BG00012 treatment at the 240-mg BID dose, the subject may continue in the study taking the 120-mg BID dose.

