11.4. Compliance

Compliance with treatment dosing is to be monitored and recorded by site staff. Compliance for BG00012 will be monitored by capsule count and captured in the eCRF.

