15.4.2. Overdose

An overdose is any dose of study treatment administered to a subject or taken by a subject that exceeds the dose assigned to the subject according to the protocol. Overdoses are not considered AEs and should not be recorded as an AE on the eCRF; however, all overdoses must be recorded on an Overdose form and faxed to Biogen SABR or designee within 24 hours of the site becoming aware of the overdose. An overdose must be reported to Biogen or designee even if the overdose does not result in an AE. If an overdose results in an AE, the AE must be recorded. If an overdose results in an SAE, both the SAE and Overdose forms must be completed and faxed to Biogen SABR or designee. All study treatment-related dosing information must be recorded on the dosing eCRF.

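### SAP 6.1.6 labels an average daily dose as compliance, so within the exposure summary a permitted 120 mg BID dose and missed capsules give the same figure

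*SAP*

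**What the plan says.** SAP 6.1.6 plans three descriptive items: "Number of days exposed to BG00012 during study 109MS311, total amount of BG00012 received and overall compliance will be summarized". It then gives the only compliance formula in either document: "Compliance for each subject is defined as the total amount of BG00012 received divided by the number of days on treatment". The SAP does not define days on treatment, does not say whether the amount received means dispensed or taken, and plans no summary of dose reductions or interruptions.

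Protocol 11.4 names a data source but gives no formula: "Compliance for BG00012 will be monitored by capsule count and captured in the eCRF".

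The assigned dose is 240 mg BID (Protocol 11.1). The protocol sets or allows a lower dose in three situations:

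- Restart after an interruption of at least 2 weeks (11.2.2): "Subjects will take one 120-mg capsule BID for 1 week".
- Flushing or gastrointestinal intolerance (11.2.6): 120 mg BID for at most 4 weeks, then a return to full dose.
- Full dose still not tolerated after that (11.2.6): "the subject may continue in the study taking the 120-mg BID dose".

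**The concern.** Compliance ought to compare what a subject took with what the subject was told to take. The SAP ratio leaves out the second quantity. For a subject who is never reduced this is only a matter of units, because dividing by 480 mg/day recovers adherence. For a subject with a protocol-directed reduction no constant divisor works, because the prescribed dose itself changes during follow-up.

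The other two items in 6.1.6 do not fill the gap. Days exposed and total amount show that the delivered dose fell below 480 mg/day, but not why. The reasons mean different things: half dose for flushing or gastrointestinal events is a tolerability finding and is permitted, whereas missed capsules are an adherence problem and noncompliance is a ground for stopping treatment (Protocol 10.1). In a long-term pediatric safety study the exposure table should keep them apart.

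The denominator is also open. If dosing is withheld for a laboratory abnormality, the SAP does not say whether those days count as days on treatment.

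**Working it through.** The plan states no numerical compliance figure, so there is nothing to reproduce. The check applies the SAP formula to constructed subjects whose dosing the protocol permits.

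**Inputs.** Treatment period 96 weeks = 672 days (Protocol synopsis). Capsule strength 120 mg (Protocol 12.1), so 4 capsules a day at 240 mg BID and 2 a day at 120 mg BID. Reduction and restart lengths are from Protocol 11.2.6 and 11.2.2. The Week 48 start and the 28-day withholding are illustrative assumptions.

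**Formulas.**

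- SAP ratio = capsules taken × 120 / days on treatment.
- Adherence = 100 × capsules taken / capsules prescribed.
- Full dose throughout: 672 × 4 = 2,688 capsules; 2,688 × 120 / 672 = 480 mg/day.

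**Why the two kinds of subject coincide.** Over T days, a fully adherent subject with d half-dose days scores 480 − 240d/T. A subject on full dose who misses m capsules scores 480 − 120m/T. The two are equal whenever m = 2d, so every permitted reduction has a missed-capsule twin.

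| Subject, 672 days on treatment | Capsules taken | SAP ratio (mg/day) | Share of 480 | Adherence |
|---|---|---|---|---|
| One 4-week reduction, none missed | 644 × 4 + 28 × 2 = 2,632 | 315,840 / 672 = 470 | 97.9% | 100% |
| 240 mg BID throughout, 56 missed | 2,632 | 470 | 97.9% | 2,632 / 2,688 = 97.9% |
| 120 mg BID from Week 48, none missed | 336 × 4 + 336 × 2 = 2,016 | 241,920 / 672 = 360 | 75.0% | 100% |
| 240 mg BID throughout, 672 missed | 2,016 | 360 | 75.0% | 2,016 / 2,688 = 75.0% |

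The Week 48 row omits the return to full dose that 11.2.6 requires before half dose may continue. With an assumed 7-day attempt it becomes 343 × 4 + 329 × 2 = 2,030 capsules, or 243,600 / 672 = 362.5 mg/day, which does not alter the point.

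**Withheld days.** Take 28 days withheld, then the 1-week restart at half dose, with none missed: 637 × 4 + 7 × 2 = 2,562 capsules = 307,440 mg.

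- Withheld days excluded: 307,440 / 644 = 477.4 mg/day.
- Withheld days counted: 307,440 / 672 = 457.5 mg/day.

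The same fully adherent subject differs by 19.9 mg/day according to a convention that the SAP does not state.

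**The case against.** The best case against acting is that almost nothing depends on this variable. The study has one arm and is descriptive (SAP 6.1). Compliance enters no analysis population (SAP 6.2.1, 6.3.1), endpoint or model. Total amount and days exposed are reported alongside, so the delivered dose is not misstated; only the label is wrong. All of this stands and limits the size of the point.

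Large discrepancies are also unlikely. Entrants must "remain on BG00012 treatment at 240 mg BID", and subjects who could not tolerate treatment in the parent study are excluded (Protocol 8.2). On the other side, a subject who missed a quarter of the capsules might not stay 96 weeks, since Protocol 10.1 allows discontinuation for noncompliance and 10.2 requires withdrawal of a subject who cannot or will not comply. This is fair: the Week 48 pair shows the mechanism and is not an expected value. A single temporary reduction moves a 96-week completer's figure by at most about 2%.

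A reader might go further and infer that the study report could not distinguish the two kinds of subject at all. The documents do not support that. SAP 6.1.3 lists major and minor protocol deviations, and substantial missed dosing could appear there while a permitted reduction would not. Neither document says that missed capsules are recorded as deviations, so the listing is not an assured remedy, but the claim has to be confined to the 6.1.6 summary.

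A reader might also take the denominator as settled, because Protocol 11.2.1 separates subjects "whether on study treatment, having dosing temporarily withheld, or permanently discontinued". That text governs the rechecking of laboratory values and does not define exposure. It leans towards excluding withheld days but does not decide the matter, so both results are shown.

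**Conclusion.** The point holds and is minor. As written, the rule gives an average daily dose under the name of compliance, and it scores a fully adherent subject on a permitted reduced dose below full compliance. Expressing the ratio as a percentage of 480 mg/day would not cure this.

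For one temporary reduction in a 96-week completer, the understatement is at most 2.1 percentage points. It reaches 25 points for half dose from Week 48, an assumed start. How often either happens is not given in the documents, so no study-level effect can be estimated and reductions should not be called common.

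It would be wrong to read this as a threat to the safety results. Counts of adverse events, serious adverse events and treatment discontinuations do not use compliance, and neither do the efficacy summaries.

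**What to change.** In SAP 6.1.6:

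1. Define compliance (%) as 100 × capsules taken (by capsule count) / capsules prescribed. Capsules prescribed are 4 a day on 240 mg BID days, 2 a day on 120 mg BID days under Protocol 11.2.2 or 11.2.6, and 0 on days withheld under the protocol. Naming capsules taken also removes the doubt about the amount received.
2. Rename the present ratio as average daily dose (mg/day), and state whether withheld days count in its denominator.
3. Optionally, report the number of subjects with any 120 mg BID dosing and their days at that dose. This is useful context but is not needed to correct the definition.

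The cost is minor SAP reprogramming: one redefined variable, one renamed variable and, if wanted, two extra table rows. It needs no protocol amendment, extra visit or subject burden. Capsule counts are already captured under Protocol 11.4, and Protocol 15.4.2 adds: "All study treatment-related dosing information must be recorded on the dosing eCRF". Neither section says that start and stop dates of prescribed 120 mg BID periods are separate eCRF fields. The low cost assumes that they are, and this should be checked before the SAP is changed.

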### **6.1.7 Visit Windows**

If a subject withdraws after receiving at least one dose of BG00012, but prior to the Week 96 scheduled visit, data from the early withdrawal visit will be assigned as the next scheduled visit if it has occurred within a visit window. Scheduled visits have a window of  $\pm 5$  days.

If more than one observation is within the same window, data closest to the target regular scheduled visit will be used in the summary statistics. If more than one observation falls in the same distance from the target regular scheduled visit day, the later observation will be used in the summary statistics.

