11.2. Modification of Dose and/or Treatment Schedule

11.2.1. Dosing Interruption for Abnormal Laboratory Values

BG00012 must be temporarily withheld and/or permanently discontinued when any of the following laboratory values meet the threshold limits defined in [Table 3](#) (laboratory abnormalities that require immediate and permanent discontinuation of study treatment are also specified in [Table 3](#)).

Table 3: Laboratory Criteria Requiring Withholding or Permanent Discontinuation of Treatment

Laboratory Parameter	Laboratory Result	Required Action
AST (SGOT) or ALT (SGPT)	$>3 \times \text{ULN}$	The Investigator should repeat the test as soon as possible. If the retest value confirms AST or ALT $>3 \times \text{ULN}$, then the study treatment must be withheld. If the value remains $>3 \times \text{ULN}$ for ≥ 4 weeks after discontinuation of study treatment, then the subject must permanently discontinue study treatment, and the event must be recorded as an AE .
Creatinine	$>1.2 \times \text{ULN}$	The Investigator should repeat the test as soon as possible. If the retest value confirms that creatinine is $>1.2 \times \text{ULN}$, then the study treatment must be withheld. If the value remains $>1.2 \times \text{ULN}$ for ≥ 4 weeks after discontinuation of study treatment, then the subject must permanently discontinue study treatment, and the event must be recorded as an AE .

CONFIDENTIAL

The information contained herein may not be used, disclosed, or published without the written consent of
Biogen MA Inc.

Laboratory Parameter	Laboratory Result	Required Action
WBC	<2000/mm ³	The Investigator should repeat the test as soon as possible. If the retest value confirms that WBC count is <2000/mm ³ , then the study treatment must be withheld. If the value remains <2000/mm ³ for ≥ 4 weeks after discontinuation of study treatment, then the subject must permanently discontinue study treatment, and the event must be recorded as an AE.
Urinalysis	Positive hematuria on microscopy	The Investigator should repeat the test as soon as possible. If retest confirms microscopic hematuria without known etiology, then the study treatment must be withheld, and urine cytology performed. If hematuria persists for ≥ 4 weeks after discontinuation or if cytology is positive for malignant cells, then the subject must permanently discontinue study treatment, and the event must be recorded as an AE. Subjects should be referred to a nephrologist for further investigation.

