#### **6.3.2.1 Definition of Baseline Value and Visit Windows**

Baseline values and visit windows for safety summaries are defined in the same way as they are for efficacy analyses (see Section 6.1.1 and 6.1.7, respectively).

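### The SAP visit-window rule lets a confirmatory retest replace the abnormal laboratory value that triggered it, biasing by-visit laboratory summaries toward normal

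*SAP*

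**What the plan says.** SAP 6.1.7 gives scheduled visits a window of ±5 days. If several observations share a window, "data closest to the target regular scheduled visit will be used in the summary statistics". For ties, "If more than one observation falls in the same distance from the target regular scheduled visit day, the later observation will be used". SAP 6.3.2.1 carries this over: "Baseline values and visit windows for safety summaries are defined in the same way as they are for efficacy analyses". Neither section mentions retests or unscheduled samples.

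Protocol 11.2.1 (version 3.0) creates such second samples:

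- Table 3, for AST/ALT, creatinine, WBC and hematuria beyond the stated limits: "The Investigator should repeat the test as soon as possible". Table 5 in Protocol 11.2.5.1 asks the same for lymphocytes below 500/mm³.
- Table 4, for on-treatment lymphocytes below the lower limit of normal: "The Investigator should repeat the test within 2 weeks".
- Subjects "must have the abnormal laboratory result rechecked at the central laboratory as follows", and Protocol 19.1.3 has one central laboratory analyze all safety samples. Retests can therefore enter the same data as scheduled samples.

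SAP 6.3.2.3 promises laboratory values and changes from baseline at each time point and lymphocyte counts at each on-treatment time point. It also promises shift tables tied to a Week 4 time point, which does not exist in the schedule (SAP Section 3, Table 1).

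**The concern.** A mandated retest exists only because the first value was abnormal, and a normal first value triggers none. Replacement by such retests therefore runs one way. A value selected for being extreme tends to be followed by a less extreme one, so the value kept is on average closer to normal. This is a selection effect rather than noise.

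It affects by-visit laboratory means and changes from baseline, the on-treatment lymphocyte counts, and the shift tables if those use windowed values. The study is single-arm and descriptive, so no comparator arm carries the same bias. Its primary objective is long-term safety, and Protocol 5.3.2 itself names severe and prolonged lymphopenia as the setting of a serious infection.

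**Working it through.** The documents give no figure for this, so there is nothing to reproduce. The selection rule can be enumerated exactly.

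**Inputs from the documents.** Window ±5 days; closest observation kept; later one if tied (SAP 6.1.7). Retest as soon as possible, with no number of days (Protocol Tables 3 and 5), or within 2 weeks (Table 4).

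**Assumptions.** The distribution of draw days and the actual retest lag r are not in the documents, so a range is shown.

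**Condition for replacement.** Let the scheduled draw fall d days before target. A retest r days later falls r − d days from target. It is kept if |r − d| ≤ d, that is, if r ≤ 2d.

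| Scheduled draw | Retest replaces it if r is at most |
|---|---|
| 5 days early | 10 days |
| 4 days early | 8 days |
| 3 days early | 6 days |
| 2 days early | 4 days |
| 1 day early | 2 days |
| On target or late | never |

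**Displacement with uniform draw days (11 days, −5 to +5).** The number of draw days on which the retest wins, by lag, is:

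- r = 1-2: 5/11 = 45%
- r = 3-4: 4/11 = 36%
- r = 5-6: 3/11 = 27%
- r = 7-8: 2/11 = 18%
- r = 9-10: 1/11 = 9%
- r = 11-14: 0

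Averaged over lags:

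- 1-7 days: (5+5+4+4+3+3+2)/(11×7) = 26/77 = 34%
- 1-14 days: (26+2+1+1)/(11×14) = 30/154 = 19%
- 7-14 days: (2+2+1+1)/(11×8) = 6/88 = 7%

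**Displacement with visits clustered on target.** With triangular weights 6 − |day| (total 36), the winning weight is 15 for r = 1-2, 10 for 3-4, 6 for 5-6, 3 for 7-8 and 1 for 9-10.

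- 1-7 days: 65/(36×7) = 26%
- 1-14 days: 70/(36×14) = 14%

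**Share due to the tie rule.** Ties occur at r = 2d. Over lags 1-7 they give 3/77 = 4 percentage points, and over 1-14 they give 5/154 = 3. The closest-to-target clause does most of the work.

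**From displacement to a visible effect (illustration only).** Let p be the true abnormal share at a visit, q the displacement share, and n the chance that a retest is normal after an abnormal first value. If every abnormal value were retested, the reported share would be p(1 − qn). Under a bivariate normal model with p = 10% and test-retest correlation 0.5, 0.7 or 0.9, n is 0.676, 0.532 or 0.311.

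- q = 26/77: 10% × (1 − 0.338 × 0.676) = 7.7%; likewise 8.2% and 8.95%
- q = 30/154: 8.7%, 9.0%, 9.4%
- q = 6/88: 9.5%, 9.6%, 9.8%

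With the scheduled-visit sample used instead, q = 0 and the share stays at 10%.

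**The case against.** The best case against is that the effect is narrow, conditional and of unknown size in a descriptive study. Much of that stands.

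- **Conditional.** Draws on or after target always keep the triggering value. Repeats of urinary casts and glycosuria come 2 weeks later (Protocol 11.2.4) and cannot displace it. A confirming retest changes no category, although the value itself may move.
- **Lag.** Table 1, footnote 11 of the protocol allows an extra visit around Day 7 so that laboratory results can be evaluated before first dispensation. That hints at slow turnaround. At lags of 7-14 days displacement is about 7%.
- **Other second samples.** A reader might infer that every second sample follows an abnormal first one. Relapse visits also draw hematology, chemistry and urinalysis (Protocol Table 2), whatever the earlier results. The one-way argument covers mandated retests only.
- **Mechanism.** A reader might also credit recovery after treatment is withheld. Under Table 3 withholding follows the confirming retest, and Tables 4 and 5 mandate no temporary withholding for lymphocytes. Regression to the mean is what remains for the confirmatory retest.

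A reader might also multiply the 19% by a retest-normal share and report the product as the share of low lymphocyte visits hidden. The documents do not support that. With assumed between-subject CV 30% and within-subject CV 15-20% (correlation 0.69-0.80), the retest-normal share is 50-62% if 5% of values are low but 20-26% if half are. The product then runs from 0.195 × 0.20 = 4% to 0.195 × 0.62 = 12%. The denominator is also wrong: once a low count is confirmed, Table 4 asks for monitoring at least every 4 weeks, which need not produce a fresh early retest at each low visit.

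None of this removes the gap. The SAP's stated rule selects the retest in identifiable cases, and mandated retests run one way.

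**Conclusion.** The point holds for by-visit laboratory summaries, and for the shift tables if they are windowed; the Week 4 reference leaves that unclear. It does not extend to by-visit safety results in general. The primary endpoint counts adverse events, serious adverse events and discontinuations per subject without visit windows (SAP 6.3.2.2). Vital signs and ECG have no mandated retest.

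The direction is toward normal on average. Under uniform draw days, displacement is about 34% for lags of 1-7 days and 19% for 1-14 days. Clustering on target lowers these to 26% and 14%, and lags of 7-14 days give about 7%. Draw-day distribution, retest lag, prevalence and test-retest correlation are all assumptions, so the net effect on any table cannot be fixed from the documents. In the illustration it ranges from slight (10% reported as 9.8%) to moderate (10% reported as 7.7%). It is worth correcting because it is systematic and avoidable.

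**What to change.** - **SAP 6.1.7 and 6.3.2.1:** state that by-visit laboratory summaries use the sample collected at the nominal scheduled visit. Retests and unscheduled samples, including relapse-visit samples, are used only when no scheduled-visit sample exists. Taking the first sample in the window is not equivalent: that could be a relapse-visit or monitoring sample. If the scheduled draw was more than 5 days early, the retest could be the only value in the window.
- **SAP 6.3.2.3:** base shift and abnormality-incidence tables on the worst post-baseline value, including retests and unscheduled samples, in place of the Week 4 time point. This fits Protocol 16.5.1.2, which asks for the incidence of shifts outside the normal range.

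The cost is two SAP sentences and some programming, with no new data. Worst-value tables will show somewhat more abnormalities, which the table titles should make clear.
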